The number and percentage of tumors achieving Technical Success will be summarized and a 95% confidence interval will be estimated. Technical Success will be evaluated based on the margin achieved after the first ablation and prior to any repeat ablations within the first 7 days.

A similar summary will be provided for Technical Efficacy. This endpoint will be based on the scan obtained at Visit 3 and will count as successes patients with A0 or A1 margins in that scan and who did not have an A2 margin since the Visit 2B scan. Additionally, if a patient received a repeat ablation for correcting a margin (to go from A1 to A0) within the first 30 days, this will also count as a success. Patients with repeat ablations to correct an A2 margin from Visit 2B to Visit 3 will not count as success for Technical Efficacy. The number and percentage of tumors with A0 and A1 margins will be presented as a subcategorization within each presentation of Technical Success and Technical Efficacy, as well as a summarization for the number and reasons for repeat ablations through Visit 3.

Local tumor progression rates at 1, 3, 6, 9, 12, 18, 24, 30, and 36 months will be estimated using the Kaplan-Meier method and 95% confidence intervals will be provided. Any repeat ablation required after Visit 3 (Month 1) will be identified as an instance of local tumor progression. A similar summary will be provided for the 36-month overall and progression-free survival rates.

Confidential Page 41 of 61

The number and percentage of patients experiencing AEs will be summarized at the preferred term level using the Society of Interventional Radiology (SIR) clinical practice guidelines for event categorization. A similar summary will also be provided for device-related AEs, procedure-related AEs, all SAEs, device-related SAEs, and procedure-related SAEs. Adverse event rates will also be estimated using cumulative patient years of exposure as the denominator as well as total number of patient ablations.

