10.2. Likelihood Analysis of Failure

In a prospective study in China, the rate of major complications (3.8% of patients) was low and no deaths occurred within 30 days of ablation. To date, more than 400 units of the Certus Microwave Ablation System and Accessories have been sold in the United States, Canada, European Union, and Singapore, where thousands of patients have been successfully treated. In recent years, MW ablation is gaining momentum in China. Because of this growing popularity of MW, failure to meet total enrolment (137 patients) in approximately 8 months, as stipulated by the protocol, is unlikely. Also, because of the low rate of major complications in patients who have been treated with MW ablation, it is unlikely that the study will be discontinued because of safety concerns.

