14.2. Serious Adverse Event

It is the investigator's responsibility to determine the "seriousness" of an AE using the protocol defined terms below. An SAE/injury is an AE that results in one or more of the following for this study:

- Resulted in death: An AE that resulted in the patient's death.
- Life-threatening illness or injury: The patient was at imminent risk of dying at the time
 of the AE.
- Permanent Impairment: An AE that resulted in permanent impairment of a body function or permanent damage to a body structure.
- Required in-patient or prolonged hospitalization. Note: If a patient has prolonged hospitalization due to having an additional ablative procedure to enhance the ablative margin and for no other adverse event, this should not be considered an SAE.
- Resulted in medical or surgical intervention to prevent life threatening illness or injury or permanent impairment to a body or body function.

Confidential Page 49 of 61

- Led to fetal distress, fetal death or congenital abnormality or birth defects.
- A persistent or significant disability or incapacity.

Notes:

- 1. Progression of the disease under study should not be reported as an SAE.
- 2. "Death" should not be reported as an SAE. The cause of death, however, should be reported as an SAE, except for progressive disease.
- 3. Planned hospitalization for a pre-existing condition is not considered an SAE.
- 4. A procedure required by the protocol is not considered an SAE unless the patient experiences a serious deterioration in health or hospitalization is prolonged.

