8.5.1 Adverse Events

An AE is defined as any undesirable clinical occurrence in a patient. An AE does not necessarily have a causal relationship with the study medical device. AEs will be recorded since date of informed consent signature until 30 days after any ablation procedure except SAEs with 36 months follow-up period.

Adverse events will be summarized by System Organ Class (SOC) and Preferred Term (PT) and broken down further by maximum severity and relationship to study device or procedure. Number (n) and percentage (%) will be presented with the percentage calculated relative to the total number of subjects in the FAS/SAF as following:

- AE Overview (subgroup by initial only and repeat ablation, run-in analysis set and full analysis set, and total count of safety analysis set)
- AE by SOC and PT
- Procedure related AE by SOC and PT
- Study device related AE by SOC and PT
- Serious AE by SOC and PT
- Procedure related serious AE by SOC and PT
- Study device related serious AE by SOC and PT
- AE by SOC, PT, and maximum severity
- AE by SIR and PT
- AE listings will be prepared. Information including SIR, PT, relationship with device/procedure, seriousness, severity, AE start and end date, intervention/treatment taken, outcome of AEwill be presented.

AEs will be coded using MedDRA Version 19.0 or higher.

Procedure-related AE

A procedure-related AE is an adverse event related to the study procedure. The relationship with study procedure is recorded as "Unlikely related", "Possibly related", "Probably related", and "Causal relationship".

Device-related AE

A device-related AE is an adverse event related to the use of the study device. The relationship with study device is recorded as "Unlikely related", "Possibly related", "Probably related" and "Causal relationship". Events marked with missing relationship with study device is considered as device-related AE.

Serious Adverse Event (SAE)

A Serious Adverse Event is any AE that:

- Resulted in death: An AE that resulted in the patient's death.
- Life-threatening illness or injury: The patient was at imminent risk of dying at the time of the AE.
- Permanent Impairment: An AE that resulted in permanent impairment of a body function or permanent damage to a body structure.

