- Required in-patient or prolonged hospitalization. Note: If a patient has prolonged hospitalization due to having an additional ablative procedure to enhance the ablative margin and for no other adverse event, this should not be considered an SAE.
- Resulted in medical or surgical intervention to prevent life threatening illness or injury or permanent impairment to a body or body function
- Led to fetal distress, fetal death or congenital abnormality or birth defects.
- A persistent or significant disability or incapacity

SAE is collected in "Adverse Events Log" CRF page with answer "Yes" to question "Is this adverse event Serious".

Procedure related SAE

A procedure related SAE meets both procedure-related AE and SAE definitions.

Study device related SAE

A study device related SAE meets both device-related AE and SAE definitions.

AE by Maximum Severity

Based on investigator's assessment, the severity of adverse events is classed as mild, moderate, or severe. Only the highest reported severity of a given adverse event is counted for the individual subject.

AE leading to Death

AE leading to death is collected in "Adverse Events Log" CRF page with answer "Fatal" to question "Outcome".

Procedure related AE Leading to Death

A procedure related AE leading to death meets both procedure related AE and AE leading to death definitions.

Study device related AE Leading to Death

A study device related AE leading to death meets both study device related AE and AE leading to death definitions.

SIR Classification System

A major complication is defined as an event that lead to substantial morbidity and disability that increases the level of care, or results in hospital admission, or substantially lengthens the hospital stay.

AE complications are classed by outcome by SIR Classification System as following:

- A. No therapy, no consequence
- B. Nominal therapy, no consequence; includes overnight admission for observation only
- C. Require therapy, minor hospitalization (< 48 hours)
- D. Require major therapy, unplanned increase in level of care prolonged hospitalization (> 48 hours)
- E. Permanent adverse sequelae
- F. Death.

The minor complications (A, B) and the major complications (C-F) will be presented by preferred term.

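### The only SIR table in SAP 8.5.1 labels all-cause class C–F events to 36 months as major complications, and no planned table gives the SIR-graded related events that protocol 8.1 calls for

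*SAP*

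**What the plan says.** SAP 8.5.1 lists one SIR output, "AE by SIR and PT", and defines its two groups: "The minor complications (A, B) and the major complications (C-F) will be presented by preferred term". Neither statement restricts onset or relationship, and the same section says that "An AE does not necessarily have a causal relationship with the study medical device". On collection it says: "AEs will be recorded since date of informed consent signature until 30 days after any ablation procedure except SAEs with 36 months follow-up period".

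Protocol 14.2 takes some events out: "Progression of the disease under study should not be reported as an SAE", and for deaths, "The cause of death, however, should be reported as an SAE, except for progressive disease".

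Protocol 8.1 (repeated in the synopsis) asks for an AE summary at preferred-term level with SIR categorisation. It then adds: "A similar summary will also be provided for device-related AEs, procedure-related AEs, all SAEs, device-related SAEs, and procedure-related SAEs". In SAP 8.5.1 the tables for related AEs and related SAEs are by SOC and PT, without SIR class.

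**The concern.** The two halves of the SIR table cover different periods. After day 30 a non-serious event is no longer collected, whereas any SAE is. An admission at month 20 for a reason unconnected with the ablation can be graded C or D and would then appear as a major complication.

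This matters because the study tests no hypothesis. Protocol 8.4 judges acceptability by a broad evaluation of all data in the context of other HCC therapies. The protocol itself cites major-complication rates: 3.8% in section 4.1.1, and 5.9% for microwave ablation in the comparison with resection in section 4.1.2. Section 10.2 pairs the first with early mortality: "the rate of major complications (3.8% of patients) was low and no deaths occurred within 30 days of ablation". A 36-month all-cause figure under the same label invites a comparison that is not like-for-like, most likely to the device's disadvantage. The table that would support a fairer comparison, SIR grade among related events, is not planned.

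**Working it through.** **Denominators (the plan's own figure).** 100 / (1 − 0.20) = 125, plus 3 × 4 = 12 run-in patients, gives 137. This reproduces SAP section 7. At 3.8% to 5.9%, procedural major complications would affect 4.8 to 7.4 of 125 patients, or 5.2 to 8.1 of 137.

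**What each SIR group can contain.**
- Up to 30 days after an ablation: all AEs, so A–B and C–F are both filled.
- From then to month 36: SAEs only. C–F keeps accruing. A–B accrues only the occasional SAE graded B, since class B includes overnight admission for observation.
- Never: disease progression or death from progression.

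**How much the late events could matter.** The documents give no rate of late unrelated class C–F SAEs, so I treat it as unknown and vary it from 0.5 to 20 patients with a first such event per 100 patient-years. Other inputs:
- Survival of 91.2% at 1 year and 72.5% at 3 years, from the multicentre study in protocol 4.1.1.
- Dropout of either none or 20% over 3 years (the 20% is from SAP section 7; spreading it evenly over 3 years is my assumption).
- Procedural rate p of 3.8% or 5.9%. Treating these as peri-procedural is an assumption, because the protocol gives neither a time window nor a relatedness rule for them.

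1. Death hazard: −ln(0.912) = 0.0921 per year in year 1, then −ln(0.725/0.912)/2 = 0.1147.
2. Person-time T from day 30 (0.0821 years) to month 36, no dropout: (0.9925 − 0.912)/0.0921 + (0.912 − 0.725)/0.1147 = 0.87 + 1.63 = 2.50 years per patient. Adding a dropout hazard of −ln(0.8)/3 = 0.0744 gives 2.25.
3. Break-even rate, where patients with a late event equal procedural ones: r = −ln(1 − p)/T. For p = 3.8%, 0.0387/2.50 = 1.5 and 0.0387/2.25 = 1.7 per 100 patient-years. For p = 5.9%, 0.0608/2.50 = 2.4 and 0.0608/2.25 = 2.7.
4. For a given rate r, q = 1 − exp(−rT). The late share is q/(q + p), and the proportion with any C–F event is 1 − (1 − p)(1 − q). The ranges below span both values of p and of T.

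| Late rate per 100 patient-years | Late share of C–F row | Patients with any C–F event |
|---|---|---|
| 0.5 | 16–25% | 4.9–7.1% |
| 1 | 27–39% | 5.9–8.2% |
| 2 | 43–56% | 8.0–10.5% |
| 5 | 64–76% | 14.0–17.0% |
| 10 | 77–85% | 23.2–26.7% |
| 20 | 86–91% | 38.7–43.0% |

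**A caution on the 3.8%.** Protocol 4.1.1 gives 8 events in a series of 221 patients, but 8/221 = 3.6%; a figure of 3.8% needs a denominator of 208 to 213. At 3.6% the break-even is 1.5 to 1.6, so the conclusion does not change.

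**The case against.** **Other outputs cover much of this.** The SAP plans procedure-related and device-related SAE tables, and SAE criteria overlap heavily with SIR C–F. The AE listing carries SIR class, relationship and dates, and the first interim is meant to describe safety to 1 month (SAP 8.6). A reader might infer that a procedural comparison is impossible; for these reasons it is not. They cover the gap only in part, however. Seriousness is not SIR class, since an overnight observation stay is class B yet may meet the hospitalisation criterion for an SAE. A count taken from a listing is not a planned estimate. SAP 8.1.6 includes all data available at the cut-off, so with about 8 months of recruitment the first interim could contain SAEs well past 1 month unless they are truncated.

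**The all-AE table follows the protocol.** Protocol 8.1 applies SIR categorisation to AEs without an onset or relatedness filter. This stands: restricting that table would remove a summary the protocol asks for, so the remedy should be additional tables.

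**A similar summary may mean only counts by preferred term.** That reading is possible. The more natural one carries the SIR categorisation over, because the sentence directly follows the SIR summary.

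**Tempting overstatements.** A reader might infer that the C–F row will consist mostly of late unrelated events, or will be several times the procedural rate. Both depend on a rate the documents do not give; at 0.5 per 100 patient-years late events are a minority. A reader might also infer that every event counts whatever its cause, but protocol 14.2 excludes progression, deaths from it and planned admissions for pre-existing conditions. Nor do the documents name 3.8% or 5.9% as safety benchmarks. Finally, SAP 8.5.1 presents C–F by preferred term and specifies no subject total, so an overall C–F rate is not an explicit output.

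**Conclusion.** The point holds on the text. The only SIR table mixes windows and causes under the label of complications, and the SIR-graded summary of related events that protocol 8.1 calls for, on its natural reading, is missing. The C–F figures are therefore not like-for-like with a peri-procedural rate.

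The mixing is built into the plan; its size is not known. The break-even of about 1.5 to 2.7 late events per 100 patient-years is low, but nothing in the documents shows whether it will be passed. It rests on the cited rates being procedural, on survival like that of the cited multicentre study, on a constant late rate independent of procedural events, and on dropout between none and 20% over 3 years.

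Two definitions need attention at the same time. SAP 8.5.1 lists four relationship categories under its related-AE definitions, starting with unlikely related, and gives no cut-off for which count. The major-complication grouping is C to E in the withdrawal criteria of protocol 7.1.5 and C–F in the SAP.

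**What to change.** In SAP 8.5.1:

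1. Keep the all-AE SIR-by-PT table, but title it all-cause SIR-graded AEs to 36 months and do not call its rows complications. Footnote the different collection windows for non-serious AEs and SAEs.
2. Add SIR-by-PT tables, with subject totals for A–B and for C–F, for (a) procedure-related and device-related AEs and SAEs, as protocol 8.1 calls for, and (b) AEs with onset within 30 days after any ablation, original or repeat. The protocol sentence also names all SAEs; one more table of the same form would complete its list.
3. State which relationship categories count as related, for procedure and for device. SAP 8.5.1 counts a missing device relationship as related but has no matching rule for the procedure.
4. Reconcile the C to E grouping in protocol 7.1.5 with the C–F grouping in the SAP.

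The cost is SAP wording and a few extra tables. Onset date, relationship and SIR class are already collected and listed for each event, so no new data are needed.

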8.5.2 Death

If any subjects that report death during the study as recorded on the "Death" CRF page, the information will be presented in a data listing

8.5.3 Laboratory Evaluations

Change from baseline at post ablation visit (V3) will be summarized.

Shift from baseline table of laboratory evaluations will be summarized descriptively by visit for each category in.

The laboratory tests are:

- Hematology (Complete Blood Count):
 - Red blood cell (RBC)

- White blood cell (WBC)
- Neutrophils (NEUT)
- Lymphocytes (LYM)
- Monocytes (MONO)
- Eosinophils(EOS)
- o Basophils
- o Platelet count
- Chemistry (Liver Function and Renal Function)
 - Aspartate Aminotransferase (AST)
 - Alanine Aminotransferase (ALT)
 - Gamma-Glutamyl Transferase (GGT)
 - o Albumin
 - o Indirect bilirubin
 - o Direct bilirubin
 - o Total bilirubin
 - o Total protein
 - o **Urea**
 - o Creatinine
 - o Sodium
 - Potassium
 - o Chloride
- Coagulation:
 - Prothrombin Time (PT)
 - Activated Partial Thromboplastin Time (APTT)
 - International Normalized Ratio (INR)

- Other:
 - Alpha-Fetoprotein (AFP)
 - o Human Chorionic Gonadotropin (HCG), Quantitative, Serum

8.5.4 ECOG Performance Status

ECOG Performance Status will be summarized descriptively by visit for each score category. A shift table of ECOG from baseline to worst post-baseline ECOG score will be presented. A listing will also be prepared.

8.5.5 Numeric Pain Rating Scale (NPRS) Pain Score

NPRS score and change from baseline will be summarized descriptively by visit. A listing will also be prepared.

8.6 Plans for Interim Analysis

There will be 2 interim analyses.

The first interim analysis will occur after all enrolled subjects have completed the 1month visit and is intended to provide an initial estimate of device effectiveness for Technical Success and Technical Efficacy as well as to summarize the perioperative out to 1-month post-operative safety profile of subjects undergoing microwave ablation.

The second interim analysis will occur after all enrolled patients have completed the 12-month visit and will include a summary of local tumor progression rates as well as safety through one year.8.7 Handling of Missing Data

There will be no imputation of data for early terminated subjects or for enrolled subjects who do not provide a measurement at a given visit.

8.8 Adjustments for Multiplicity

Not applicable.

8.9 Subgroup Analysis

The subjects in Full Analysis Set are grouped by the number of ablation procedures:

• The initial only group contains all subjects who only receive the initial, planned ablation procedure at Visit 2A.

 The repeated group contains all subjects who receive a repeat ablation in the first 30 days

Subgroup analysis for Tumor type(primary HCC and recurrent HCC and other) for technical success and technical efficacy (analyzed for patient level and tumor level).

For subgroup analysis, the percentage and 95% CI will be provided by using forest plot.

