Microwave ablation (using the Certus Microwave Ablation System only) may be performed for recurrence of target tumor(s) or to achieve complete tumor ablation with adequate margin (A0) of the target tumor(s) if the initial ablation had an insufficient margin, if the treating physician deems appropriate and necessary. While repeat ablations for a recurrence may be conducted at any point during the study duration, repeat ablations to correct an ablative margin may only be performed within the first 30 days of the original ablation (by Visit 3).

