8. STATISTICAL CONSIDERATIONS

8.1. Statistical Design, Method and Analysis Procedure

This is a single-arm, prospective, multicenter study designed to evaluate the efficacy and safety of the NeuWave Certus Microwave Ablation System in the treatment of Chinese patients

Confidential Page 40 of 61

who have a single HCC tumor up to 5 cm or who have a maximum of 3 HCC tumors of up to 3 cm per tumor.

Categorical variables will be summarized descriptively by frequencies and associated percentages. Continuous variables will be summarized descriptively by number of patients, mean, standard deviation, median, minimum, and maximum. Confidence intervals will also be provided for procedure-related variables. A detailed Statistical Analysis Plan (SAP) describing all planned analyses of data collected in this study will be finalized prior to any analysis of data.

There will be three analysis populations defined for summary of data collected in this study. The primary analysis of safety and effectiveness endpoints will be performed on the Full Analysis Set, defined as all patients who are enrolled in the study, are not part of the run-in phase, and have the NeuWave Microwave Ablation System used for ablation. A Per Protocol analysis set will be defined as all patients in the Full Analysis Set who have no major protocol deviations. Effectiveness analyses will be repeated for the Per Protocol Set. The Safety Set will include all patients who provide informed consent and have MW ablation attempted with the NeuWave system and includes run-in phase patients. The Safety Set will be used for summarization of safety endpoints only. Safety and effectiveness data collected on patients participating in the run-in phase may be summarized separately from the remaining patients. There will be at least one planned subgroup analysis based on whether or not patients have a repeat ablation in the first 30 days to correct a margin (A1 to A0). A summary of all efficacy endpoints as well as adverse event summaries will be provided for all patients who only have the initial, planned ablation procedure at Visit 2A. These summaries will also be provided for all patients who receive a repeat ablation in the first 30 days.

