A subject archieving technical efficacy is defined as a patient with all tumors reaching A0 or A1 at Visit 3. The number and percentage of subjects archieving Technical Efficacy will be summaried as well. Percentage will be calculated relative to the total number of subjects in relavent analysis population (FAS or PPS). A 95% confidence interval will be estimated using wald method. But the subjects who have any A2 margin since the visit 2B scan would not be counted as technical efficacy regardless if the tumor was corrected with repeat ablation.

Local tumor progression (LTP) (the 2nd interim, final)

LTP is evaluated after the ablation of the target tumor(s). LTP describes the appearance of tumor foci at the edge of the ablation zone, after at least one contrast-enhanced follow-up

MRI scan has documented adequate ablation, and an absence of viable tissue in the target tumor and surrounding ablation margin, by using imaging criteria.

Tumor-level analysis method is same as that of Technical Success endpoint. The number and percentage of tumors with LTP will be summarized and a 95% confidence interval will be estimated using Wald method.

A subject with LTP is defined as a patient with any target tumor LTP. The number and percentage of subjects with LTP. Percentage will be calculated relative to the total number of subjects in relevant analysis population (FAS or PPS).

Subgroup analysis is defined in SAP section 8.11. Two subgroup columns (subjects/tumors with only initial ablation and subjects/tumors with repeat ablation) and 1 total column will be used as analysis columns in LTP tables.

Tumor type (primary HCC and recurrent HCC and other) will be another subgroup variable for LTP (analyzed for patient level and tumor level).

LTP start date is the date of initial ablation of a subject. The event date of LTP is collected in "Ablation Zone Assessment" CRF page as following table:

		Event/Censoring	
	Situation	Date	Outcome
No post-base	eline or no baseline Ablation Zone A	ssessment	
	No post-baseline local tumor	Date of initial	
A1	evaluation	ablation	Censored
	No baseline local tumor	Date of initial	
A2	evaluation	ablation	Censored
With baselin	e and post-baseline tumor assessm	ents	
	Local Tumor Progression and zero or one missed tumor assessment prior to confirmed		
B1	LTP	Date of first LTP date	Event

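### Read literally, SAP 8.9 leaves patients first re-ablated after day 30 in neither ablation subgroup, which lowers the initial-only LTP rate

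*SAP*

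**What the plan says.** Protocol 8.1 names one subgroup analysis and applies it to all efficacy endpoints and the adverse event summaries. It introduces the analysis as a yes/no split, "based on whether or not patients have a repeat ablation in the first 30 days to correct a margin (A1 to A0". It then says that one set of summaries is "for all patients who only have the initial, planned ablation procedure at Visit 2A", with a second set for patients re-ablated in the first 30 days.

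SAP 8.9 keeps the second form and says that grouping is by number of procedures:

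- "The initial only group contains all subjects who only receive the initial, planned ablation procedure at Visit 2A" (no time limit)
- "The repeated group contains all subjects who receive a repeat ablation in the first 30 days" (30-day limit)

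For LTP, SAP 8.4.1 makes the subgroup the table layout: "Two subgroup columns (subjects/tumors with only initial ablation and subjects/tumors with repeat ablation) and 1 total column". These labels carry no window. The text adds "Subgroup analysis is defined in SAP section 8.11", but section 8 of the SAP ends at 8.10 and the subgroups are in 8.9. An initial-versus-repeat split is also used for Health Economics (SAP 8.4.1) and for the AE overview (SAP 8.5.1).

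The rules on repeat ablation are in the protocol. Section 7.2.2 allows re-ablation for recurrence throughout the study and margin correction only within 30 days, in each case "if the treating physician deems appropriate and necessary". Section 7.2.4 restricts repeats to target tumors. Section 8.1 adds: "Any repeat ablation required after Visit 3 (Month 1) will be identified as an instance of local tumor progression".

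**The concern.** The two SAP 8.9 definitions do not cover the whole FAS. A patient with no early repeat who is re-ablated at, say, month 9 has had more than the Visit 2A procedure, so is not initial-only. The repeat was not in the first 30 days, so the patient is not in the repeated group either.

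The patients lost this way are not a random subset. After day 30 a repeat can only be for recurrence of a target tumor, and after Visit 3 it is LTP by definition. Membership of the initial-only group therefore depends on the outcome tabulated in that column. The repeated group keeps all its LTP cases, so the comparison is tilted in favor of a single ablation.

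Two other endpoints are affected. Progression-free survival counts local progression, so its initial-only column loses the same events. The secondary efficacy rate is calculated among subjects with LTP who were re-ablated, so its initial-only denominator is empty.

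The undated column labels in SAP 8.4.1 permit another reading, in which any repeat at any time puts the patient in the repeat column. The initial-only rate is then just as low, and the repeat column is inflated as well.

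**Working it through.** **Plan's own figures.** 100/(1 − 0.20) = 125 patients after the run-in, and 125 + 4 × 3 = 137 in total. Both agree with Protocol 8.2.1 and SAP 7. The plan gives no figure for the subgroups, so the rest is illustration.

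**Inputs.**

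- N = 125, the FAS size if every post-run-in patient is ablated.
- L, the LTP rate among patients without an early repeat. Not given; 10% and 20% are assumed. The only LTP rate in the protocol is the 5.9% cited in section 4.1.1. It is per tumor, at a mean follow-up of 17.3 months, and is printed beside 78/1363, which is 5.7%. It is used here as a low case.
- r, the share of those LTP cases re-ablated later. Not given; assumed.
- e, the share of patients with a repeat in the first 30 days. Not given; 10% is assumed, with 5% and 20% as alternatives.

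All calculations are crude per-patient proportions. Every late re-ablation is taken to fall after Visit 3.

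**Literal reading of SAP 8.9.** Re-ablated LTP cases leave both numerator and denominator, so the initial-only column shows (1 − r)L / (1 − rL). For L = 10% and r = 50% this is 0.05/0.95 = 5.3%.

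| Assumed L | r = 0 | r = 25% | r = 50% | r = 75% |
|---|---|---|---|---|
| 5.9% | 5.9% | 4.5% | 3.0% | 1.5% |
| 10% | 10.0% | 7.7% | 5.3% | 2.7% |
| 20% | 20.0% | 15.8% | 11.1% | 5.9% |

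These percentages depend on neither N nor e. The shown rate is below L whenever r > 0 and L < 100%.

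**Patients in neither group.** The number is N(1 − e)rL = 112.5 × rL at e = 10%.

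| Assumed L | r = 25% | r = 50% | r = 75% |
|---|---|---|---|
| 5.9% | 1.7 | 3.3 | 5.0 |
| 10% | 2.8 | 5.6 | 8.4 |
| 20% | 5.6 | 11.25 | 16.9 |

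**Any-repeat reading of SAP 8.4.1.** The initial-only column is as in the first table. If early-repeat patients have the same L, the repeat column shows [eL + (1 − e)rL] / [e + (1 − e)rL]. For e = 10%, L = 10% and r = 50% this is (0.01 + 0.045)/(0.10 + 0.045) = 37.9%, where the 30-day split would show 10%.

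| Assumed L (e = 10%) | r = 25% | r = 50% | r = 75% |
|---|---|---|---|
| 10% | 26.5% | 37.9% | 46.3% |
| 20% | 44.8% | 57.9% | 66.0% |

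At L = 10% and r = 50% the repeat column shows 53.8% if e = 5% and 25.0% if e = 20%.

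**30-day yes/no split.** The two groups add up to the FAS, and the no-early-repeat column shows L itself whatever r is.

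**The case against.** The strongest counter-argument is that the intended split can be recovered. The opening sentence of Protocol 8.1 is an exhaustive 30-day yes/no division, and the later wording can be read as a loose description of the *no* arm. On that reading a patient re-ablated at month 9 stays in that arm and nothing is biased. The LTP columns can likewise be read as inheriting the 30-day rule, since SAP 8.4.1 refers to a subgroup section for the definition. That makes the any-repeat figures the less likely case, and they need the further assumptions about e and equal L.

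This may well be what was meant, but it does not settle what will be programmed. The next sentence of Protocol 8.1 and the SAP 8.9 definition both use the open-ended wording. SAP 8.9 says it groups by number of procedures, and the 8.4.1 labels are undated and cite a section that does not exist. The text supports three different datasets.

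Four limits do stand:

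- There is no bias if no LTP case is re-ablated late, and the true share is unknown.
- At the protocol's cited 5.9% the absolute shifts are smaller.
- The analyses are descriptive, with no hypothesis test or acceptance criterion. Technical Success and Technical Efficacy are essentially settled by Visit 3.
- The Visit 3 window extends 7 days past one month. A repeat after day 30 but before a late Visit 3 is in neither group without automatically being LTP.

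**Conclusion.** The concern holds. As written, SAP 8.9 leaves patients first re-ablated after day 30 unclassified, and those first re-ablated after Visit 3 are all LTP cases. If any LTP case without an early repeat is re-ablated after Visit 3, the initial-only LTP rate is understated, apart from the small Visit 3 window effect noted above. With half of the LTP cases re-ablated, the shown rate is roughly half the true one across the assumed range of 5.9% to 20%. The direction follows from the definitions. The size rests on assumed LTP and re-ablation rates and on crude per-patient proportions rather than Kaplan-Meier or tumor-level estimates.

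The damage is limited to the subgroup columns, and the total FAS LTP estimate does not change. It should still be corrected, because this is the one subgroup the protocol names and it covers every efficacy endpoint.

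**What to change.** In SAP 8.9, define the groups as no repeat ablation within 30 days of the original ablation versus at least one repeat within those 30 days. State that a later re-ablation never changes a patient's group. In SAP 8.4.1, say that the LTP columns use this definition and correct the cross-reference from 8.11 to 8.9. The Health Economics and AE overview splits should refer to the same definition or state their own.

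One conflict needs a decision. Protocol 8.1 limits the early repeat to correction of a margin from A1 to A0, while SAP 8.9 counts any repeat in the first 30 days. A patient re-ablated early for an A2 result is therefore classified differently in the two documents. The sponsor should choose one rule and use it in both.

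A day-30 landmark for the time-to-event curves in this comparison is optional.

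The cost is two sentences in SAP 8.9, one corrected reference and a short statement on the columns in SAP 8.4.1, and the wording that settles the A1-to-A0 question. Protocol 8.7 allows such changes in an amended SAP. No new data are needed, no patients are dropped, and the time origin stays the same.
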